### 7.2. Eligibility criteria

#### 7.2.1. Inclusion criteria

- Signed informed consent before any study specific procedures
- Able to read and understand Danish
- Male or female age between 18 and 85 years
- The researcher believes that the participant understands what the study entails, is capable of following instructions, can attend when needed, and is expected to complete the study
- The investigator will ensure that fertile female participants have a negative pregnancy test before treatment initiation and use contraception during the study period. The following methods of contraception, if properly used, are generally considered reliable: oral contraceptives, patch contraceptives, injection contraceptives, vaginal contraceptive ring, intrauterine device, surgical sterilization (bilateral tubal ligation), vasectomized partner, double barrier (condom and pessary), or sexual abstinence. Methods of contraception will be documented in the source documents
- Within the current hospital admission and prior to inclusion, the patient must fulfill at least two of the following criteria to establish a diagnosis of AP (according to the revised Atlanta criteria (20)): i) abdominal pain consistent with AP (acute onset of a persistent, severe, epigastric pain often radiating

to the back); ii) serum amylase activity at least three times greater than the upper limit of normal; and iii) characteristic findings of AP on diagnostic imaging

- Predicted moderate or severe AP based on the fulfillment of 2 or more SIRS criteria within the last 24 hours prior to inclusion (see figure 2)

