## 7.5. Participant timeline

### 7.5.1. Study days

A detailed description of the study procedures is illustrated in Table 1. Patients will be evaluated daily during admission by medical personnel and treated in agreement with the IAP/APA evidence-based guidelines for the management of AP (2). As part of the study, they will receive daily infusions with methylnaltrexone or matching placebo, and have the following examinations performed: i) clinical outcome and patient symptoms will be evaluated by means of both well-validated questionnaires and information from the patient's medical records (see section 9.1.2.), ii) the PASS score will be obtained daily and used to document the primary endpoint 48 hours after randomization, iii) blood samples (including C-Reactive Protein (CRP), interleukin (IL)-6, IL-8, IL-18, tumor necrosis factor alpha (TNF- $\alpha$ ) and cluster of differentiation 163 (CD163)) will be drawn

daily with the purpose of evaluating the systemic inflammatory response, and iv) an abdominal contrast-enhanced CT study will be performed at inclusion and after conclusion of treatment at day 5 (+/- 1 day) to document the presence and extent of pancreatic inflammation, fluid collections and necrosis according to the definitions given in the revised Atlanta criteria (20). As an integrated part of the CT exam at day 5 (+/- 1 day) patients will undergo assessment of the colon/gut transit time using radiopaque markers given orally in the morning on day 3 up to the planned CT exam. Finally, the intestinal permeability will be evaluated by a polyethylene glycol (PEG) 400/4000 test (see section 9.1.5.) 48 hours after randomization. At hospital discharge, patients are invited for a follow-up visit on day 14 (+/- 2 days) after randomization where the outcomes assessed during hospital admission (blood test and questionnaires including the PASS score) will be reassessed. Patients ready for discharge prior to completing five days treatment with methylnaltrexone will be handled according to the following:

- < 48 h of treatment: All data collection will be terminated upon discontinuation of the study medication and participant is regarded as dropout.

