#### 9.1.2. Clinical outcome and health resource utilization

Clinical outcomes and health resource utilization are documented using preformed questionnaires and by means of the medical records. Thus, participants will be asked to fill out three questionnaires daily: i) The modified Brief Pain Inventory short form, ii) Bristol Stool Form Scale and iii) Gastrointestinal Symptom Rating Scale (GSRS). For a detailed description of these, see below. From the patients' medical records, the following will be registered: i) presence of local and systemic complications as well as organ failure (transient or persistent), used to classify the severity of AP according to the revised Atlanta criteria (20), ii) need for intensive care unit admission, iii) need for analgesics, iv) nutritional support, v) invasive treatment, vi) duration of hospitalization, and vii) mortality. Total duration of hospitalization, readmission rates and mortality will be determined retrospectively 30 and 90 days after admission using the patients' medical records.

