2.2. Secondary Objectives and Outcomes

The secondary objective is to document the effects of methylnaltrexone treatment on several clinical outcomes in patients with acute pancreatitis.

The secondary outcomes are listed below:

- Difference between treatment groups (methylnaltrexone or placebo) in daily PASS-scores during treatment and at 14-day follow-up
- Difference between treatment groups on disease severity assessed using the revised Atlanta criteria (10), where patients are put into one of three categories (mild/moderate/severe)
- Difference between treatment groups on subjective measures of pain intensity and gastrointestinal function assessed using validated questionnaires (13–15) daily during treatment and at 14-day follow-up
- Difference between treatment groups in length of admission and mortality, assessed retrospectively 90 days after admission, using the patients' medical records

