- Pre-existing renal insufficiency (defined as habitual estimated glomerular filtration rate (eGFR) below 45 ml/min/1,73m²)
- End-stage renal impairment requiring dialysis prior to inclusion
- Severe pre-existing comorbidities (assessed by investigator upon inclusion)
- Severe non-pancreaticobiliary infections or sepsis caused by non-pancreaticobiliary disease
- Child-Pugh class B or C liver cirrhosis
- Lactating

5. Data handling

Outcome	Source	Data collection rate	Datatype
PASS-score	From the patients' medical records (vital signs, lab results, quantification of need for opioid treatment), self-reported pain intensity and self-reported tolerance to solid foods	Daily during treatment and at 14-day follow-up	Ratio
Disease severity	Stratified as mild/moderate/severe using information about complications and organ failure from medical files	At 14-day follow-up	Ordinal
Subjective measures of pain intensity	Questionnaire: Pain intensity (current + worst/least pain the past 24 hours using NRS), pain interference score (7 parameters, scores 0-10)	Daily during treatment and at 14-day follow-up	Ordinal
Length of admission	Medical records, no. of days	90 days after randomization	Ratio
Mortality	Medical records; deceased y/n	90 days after randomization	Nominal
Circulating levels of pro- and anti-inflammatory cytokines,	Blood samples	Daily during treatment and at 14-day follow-up	Ratio
Intestinal permeability, gut transit time	Urine samples, CT-scans	Once during treatment (day 2-3)	Ratio
Prevalence of pancreatic complications	Stratified according to the revised Atlanta criteria (21) based on CT-scan	On day 5	Ordinal

Table 1

Delegated trial personnel at each trial center will register the collected data in the electronic case report form (eCRF) using the electronic data capture tool REDCap (Research Electronic Data Capture, version 10.6.26) hosted by the organization of The North Denmark Region. REDCap is a secure browser-based software, which meets all regulatory safety requirements (22,23). Data recording will begin when a participant is included and will occur gradually to the end of the trial. A detailed record of any corrections will be kept within REDCap. REDCap also contains features to improve data validation in the form of predefined variable ranges, options to detect that dates are in correct order and warnings if the forms are not sufficiently filled in.

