6.2. Secondary and exploratory analyses

Secondary and exploratory outcomes will be presented graphically to illustrate trends and potential differences between groups. Thus, outcomes measured repeatedly (PASS-score and levels of pro- and anti-inflammatory cytokines) will be illustrated using trend curves for each treatment group with single time points represented as mean and standard deviation or median and interquartile range, depending on normality. Single time point outcomes will be presented using boxplots depicting the difference between mean and standard deviation or median and interquartile range, depending on normality. Statistical analysis will also be performed for these outcomes according to below.

Repeated measures (e.g. daily PASS-scores, levels of pro- and anti-inflammatory cytokines, subjective measures of pain intensity)

For analysis of repeatedly measured secondary outcomes (daily PASS-scores, daily levels of pro- and anti-inflammatory cytokines), a repeated measures linear mixed-effects model will be used, as described for the primary endpoint. Furthermore, summary statistics and trend curves of PASS scores will be provided for the individual time points.

Single time point outcomes (length of admission, intestinal permeability and gut transit time)

Single time point outcomes (length of admission, measures of gut permeability and transit time) will be compared between groups using the two-sample unpaired t-test, when normality can be confirmed using the Shapiro-Wilk test, or the non-parametric analysis Mann-Whitney U-test when normality cannot be confirmed.

Counted data (disease severity, mortality)

After each patient has been placed in one of three categories (mild/moderate/severe), we will assess whether the prevalence of ‘moderate-to-severe’ disease is different between the two treatment groups. Thus, a 2 x 2 contingency table will be calculated (‘experienced event’ (D) being moderate or severe disease, ‘did not experience event’ (H) being mild disease and the χ^2 test will be employed to test the null hypothesis of no difference between groups.

Mortality between groups (assessed 90 days after randomization) will be analyzed using a 2 x 2 contingency table (‘experienced event’ (D) being death, ‘did not experience event’ (H) being survival). As we expect few of our patients to die during the study period, we plan to use Fishers exact test to test the null hypothesis of no difference between groups.

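### The Atlanta severity test ignores status at randomization, so patients already moderate or severe at entry dilute the comparison and cost power

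*SAP*

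**What the plan says.** **Outcome and test.** SAP 2.2 lists the revised Atlanta severity category directly after the daily PASS scores. SAP 6.2 (counted data) then says: "After each patient has been placed in one of three categories (mild/moderate/severe), we will assess whether the prevalence of" moderate-to-severe disease differs between the arms. The event is defined as "being moderate or severe disease", mild disease is the non-event, and the chi-square "test will be employed to test the null hypothesis of no difference between groups". No covariate or stratum is named. Protocol 9.3 names Fisher's exact test for binary outcomes, which is also unadjusted.

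**How the grade is obtained.** SAP section 5, Table 1 describes it as "Stratified as mild/moderate/severe using information about complications and organ failure from medical files", recorded at the 14-day follow-up. Protocol 9.1.2 takes from the medical records the "presence of local and systemic complications as well as organ failure (transient or persistent), used to classify the severity of AP". Neither place gives a start to the observation window.

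**Who can enter.** Protocol 7.2.1 requires "Predicted moderate or severe AP based on the fulfillment of 2 or more SIRS criteria within the last 24 hours prior to inclusion". The renal exclusions in Protocol 7.2.2 and SAP 4.1 concern habitual eGFR below 45 and dialysis before inclusion. Acute organ failure, fluid collections and necrosis from the current attack are not excluded.

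**What is known at entry.** Protocol 7.5.1 states that "an abdominal contrast-enhanced CT study will be performed at inclusion". Table 1 of the Protocol schedules a baseline PASS, which scores organ failure. SAP 6.1 uses baseline PASS as a covariate for PASS. Nothing comparable is planned for severity, and entry organ failure and CT status are not among the descriptive variables in SAP 2.4.

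**The concern.** A patient who already has organ failure or a local complication when randomized is counted as an event whatever the treatment then does. Such patients add to the event count in both arms but carry no information about the drug. They pull the two proportions together and add noise.

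In a 90-patient trial this matters for interpretation. SAP 2.5 names reduced disease severity as the first expected benefit. A flat result on the Atlanta grade could be read as no effect on severity when part of the outcome was settled at entry. The data needed to separate the two are collected but not used for this test.

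**Working it through.** **The plan's own figure.** The only sample-size figure is for PASS: difference 25, SD 40, 80% power, two-sided 0.05. n = 2 x (1.960 + 0.842)^2 x 40^2 / 25^2 = 40.2, so 41 per group, as stated, raised to 45. No figure is given for the severity endpoint.

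**Inputs.** From the documents: 45 per arm, unadjusted chi-square, moderate or severe counted as the event. Assumed, because the documents are silent:
- q, the share already meeting moderate/severe criteria at randomization;
- the new-event risk among the rest, 50% on placebo, with 20% (large effect) or 35% (smaller effect) on methylnaltrexone;
- that any organ failure or complication lifts a patient out of the mild category (the grading rules are in a cited source).

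The one complication rate in the documents, about 20% in Protocol 6.1, is for all acute pancreatitis and is not split by time of onset, so it does not supply q.

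**Dilution.** With new-event risks c (placebo) and t (active), the analysed risks are q + (1 - q)c and q + (1 - q)t. Their difference is (1 - q)(c - t). At q = 0.30, c = 0.50, t = 0.20:
- placebo 0.30 + 0.70 x 0.50 = 0.65; active 0.30 + 0.70 x 0.20 = 0.44;
- risk difference 0.21, which is 0.70 x 0.30;
- risk ratio 0.44/0.65 = 0.68, against 0.20/0.50 = 0.40 for new events;
- 0.30/0.65 = 46% of placebo-arm events are fixed before treatment.

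**Why stratifying helps.** In the stratum already meeting the criteria everyone is an event, so observed minus expected and the variance are both zero. The Cochran-Mantel-Haenszel statistic therefore comes only from patients whose outcome was still open, though all patients stay in the analysis.

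**Power, 45 per arm.** Simulation, 200,000 trials per setting: entry events binomial(45, q) in each arm, new events binomial among the rest, no continuity correction. A repeat run agreed to within one percentage point.

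| q | 50% v 20%: as written | 50% v 20%: stratified | 50% v 35%: as written | 50% v 35%: stratified |
|---|---|---|---|---|
| 5% | 81% | 84% | 26% | 29% |
| 10% | 74% | 82% | 24% | 28% |
| 20% | 62% | 78% | 20% | 25% |
| 30% | 50% | 72% | 17% | 22% |
| 40% | 42% | 65% | 15% | 20% |

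Hand check at q = 30%, large effect, normal approximation. As written: (0.21 - 1.96 x 0.1050)/0.1026 = 0.04, power 52%. With 0.70 x 45 = 31.5 open patients per arm: (0.30 - 1.96 x 0.1202)/0.1141 = 0.56, power 71%. Both agree with the table.

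**Type I error.** Exact enumeration of the planned chi-square at 45 per arm gives 4.5%, 4.9% and 5.3% for common event rates of 0.5, 0.6 and 0.7.

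**Analysis set.** SAP 2.5 analyses secondary endpoints per protocol (more than 75% of study drug, no major deviation). That set is smaller than 45 per arm, so every power above would be lower in practice.

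**The case against.** **The share at entry may be small.** Participants must give consent, follow instructions and be expected to finish; treatment is described as covering the first days of admission; and SIRS identifies patients at risk of worse disease. A reader might infer from the SIRS criterion that many patients are already moderate or severe at entry. The documents do not support that: it is a prediction, and q is not given. At q = 5% the loss is about 3 points for either assumed effect. This stands as a limit on size. It does not remove the mechanism, because nothing excludes acute organ failure at entry. Protocol 7.3.1 even carries a rule for eGFR below 30 although habitual eGFR below 45 is an exclusion.

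**Chance imbalance.** A reader might also infer that an imbalance in entry status would produce false positives. It would not, beyond the nominal rate: randomization balances q in expectation, and the test's error already allows for chance imbalance (about 5% as calculated).

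**The plan already has some protection.** Protocol 9.3 compares baseline characteristics and allows covariate analyses where relevant subgroup differences are evident. SAP 2.5.2 says secondary endpoints are assessed at baseline, but its Table 1 lists severity only at the 14-day follow-up. The primary PASS model adjusts for baseline PASS. These are fair points, but none fixes a baseline-adjusted severity test in advance.

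**The Atlanta category is the stated outcome.** Redefining the event as new or worse after randomization would change that outcome, and worse would need its own definition. This objection stands and shapes the fix. It does not touch a stratified test, which leaves the grade unchanged.

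**Conclusion.** The point holds as a loss of power and an attenuated estimate on one secondary endpoint. The primary PASS analysis is not affected and type I error is not inflated. The factor (1 - q) is exact once an entry feature fixes the grade; the power figures rest on assumed values of q and of the effect. Over q = 5% to 40%, stratifying gains roughly 3 to 23 points if the effect is large (50% v 20%) and 3 to 5 points if it is smaller (50% v 35%). In the second case both tests remain badly underpowered, so the change would not make the endpoint decisive. It is still worth making because it uses data already collected and keeps both the outcome and all patients in the analysis.

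**What to change.** In SAP 6.2:

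1. Keep the revised Atlanta grade as the outcome, and state the window over which complications and organ failure are counted.
2. Derive one binary variable, moderate/severe criteria already met at randomization, from the inclusion CT and the baseline organ-failure assessment. Say how a missing inclusion CT is handled.
3. Replace the plain chi-square with a Cochran-Mantel-Haenszel test stratified by that variable. Report event proportions by arm within each stratum, since the overall risk difference stays diluted by (1 - q) whichever test is used.
4. Add entry status by arm to the baseline table (SAP 2.4).
5. If wanted, report new or worse events after randomization as a supportive analysis, with worse defined in advance. It should not replace the stated outcome.

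The cost is SAP wording and one derived variable, both to be settled before unblinding. No new data or visits are needed. If no patient meets the criteria at entry, the stratified test reduces to almost the same test as now planned.

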6.3. Major Protocol Deviations

It is expected that a proportion of the patients included into the study, will recover before 5 days have passed and thus be discharged before completing the study protocol. In case of early discharge, data handling of both primary and secondary outcomes be stratified according to table 2:

< 48 hours of treatment	All data collection will be terminated upon discontinuation participant is regarded as dropout.
\geq 48 hours of treatment, but discharge before day 5	Participant will be lost to follow-up on the following outcomes: daily PASS scores, blood samples, vital signs. The participant will be asked to complete questionnaires at home, and they will be offered a follow-up CT scan in an outpatient setting on day 5 (+/- 1 day). Furthermore, they will be invited to participate in the 14-day follow-up and mortality will be registered retrospectively.

Table 2

For the statistical analyses, the Last-Observation-Carried-Forward method will be employed in case of early hospital discharge or other reasons for missing values. We expect most missing values to be a consequence of early discharge (~ recovering early from their disease) and thus the Last-Observation-Carried-Forward method will reflect this by carrying forward a value corresponding to low disease activity after discharge, which we find to be a fair assumption. If this is not the case, e.g. if a lot of missing values are due to severe disease, we will consider using other methods for imputation of missing values.

7. Implementation of Analysis Plan

A monitor will be allocated from the good clinical practice (GCP) unit at Aarhus and Aalborg University Hospitals, and the responsible monitor will contact and visit the principal investigator on a regular basis. The monitor will be authorized to inspect the different study records (CRFs,

Aalborg, Denmark

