- ≥ 48 h of treatment, but discharge before day 5: Participant will be lost to follow-up on the following outcomes: daily PASS scores, blood samples, vital signs, quantification of need for analgesics, nutritional support, intravenous fluid resuscitation and antibiotics, and data will be analyzed using the Last-Observation-Carried-Forward method (see section 9.3.). The participant will be asked to complete questionnaires at home and they will be offered a follow-up CT scan in an outpatient setting on day 5 (+/- 1 day). Furthermore, they will be invited to participate in the 14-day follow-up and readmission rates as well as mortality will be registered retrospectively.

Randomization	Methylnaltrexone or placebo (0.15 mg/kg/day)				End of study	Follow-up
Baseline	24±2 hours	48±2 hours	72±2 hours	96±2 hours	120±2 hours	14±2 days
PASS	PASS	PASS	PASS	PASS	PASS	PASS
Clinical outcome	Clinical outcome	Clinical outcome	Clinical outcome	Clinical outcome	Clinical outcome	Clinical outcome
Blood samples	Blood samples	Blood samples	Blood samples	Blood samples	Blood samples	Blood samples
		Intestinal permeability		Intestinal transit time		

Computed tomography				Computed tomography	Health resource utilization
---------------------	--	--	--	---------------------	-----------------------------

**Table 1:** Participant timeline. PASS; pancreatitis activity scoring system.

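### The SAP leaves out the readmissions that the protocol records, does not define length of admission, and carries PASS forward after discharge even for a patient who is readmitted

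*SAP*

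**What the plan says.** Protocol 7.5.1 covers patients discharged after at least 48 h of study treatment but before day 5. They stop contributing daily PASS scores, but "they will be invited to participate in the 14-day follow-up and readmission rates as well as mortality will be registered retrospectively". Protocol 9.1.2, which is not limited to early discharges, adds: "Total duration of hospitalization, readmission rates and mortality will be determined retrospectively 30 and 90 days after admission".

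SAP Table 2 (section 6.3) restates the early-discharge rule as "they will be invited to participate in the 14-day follow-up and mortality will be registered retrospectively"; readmission is gone. The SAP's secondary outcome on hospital stay is "Difference between treatment groups in length of admission and mortality, assessed retrospectively 90 days after admission". Its data table (SAP section 5, Table 1) describes length of admission only as "Medical records, no. of days", looked up at 90 days. SAP 6.2 then says: "Single time point outcomes (length of admission, measures of gut permeability and transit time) will be compared between groups". No SAP outcome, data item or analysis concerns readmission.

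For missing values after early discharge, SAP 6.3 uses last observation carried forward (LOCF). It argues that this means "carrying forward a value corresponding to low disease activity after discharge, which we find to be a fair assumption". It makes no exception for a patient who comes back.

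**The concern.** SAP 2.5 expects that methylnaltrexone may bring discharge forward, and it counts a shorter stay as a benefit. A plan that rewards earlier discharge needs readmission reported beside it; otherwise an arm that discharges sooner and readmits more could look better than it is. Readmission is also the most direct check on the SAP's reason for LOCF. A patient back in hospital before 120 h is evidence against low disease activity, yet the plan would still fill that patient's later scores from before discharge. The protocol already plans to collect the information, and the SAP gives no reason for leaving it out.

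**Working it through.** **1. The two documents side by side**

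| Item | Protocol | SAP |
|---|---|---|
| Still recorded after discharge at 48 h or later but before day 5 | 7.5.1: 14-day visit, readmission, mortality | Table 2: 14-day visit, mortality |
| Record look-up | 9.1.2: total hospital duration, readmission, mortality, at 30 and 90 days | 2.2 and Table 1: length of admission, mortality, at 90 days |
| Meaning of the stay variable | Total duration | Number of days; index stay or total not stated |
| Readmission as an outcome | Not named in 7.4.2; a data item in 7.5.1 and 9.1.2 | Absent |

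**2. Which PASS values are affected**

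PASS is due at 24, 48, 72, 96 and 120 h and at day 14 (Protocol Table 1). A patient treated for at least 48 h has an observed 48 h score. A patient treated for less is a dropout and is replaced. LOCF therefore fills 72 to 120 h, and day 14 only if that visit is missed. For a discharge at 60 h, the last scheduled score is the one at 48 h, and it fills 72, 96 and 120 h.

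**3. Which analysis set is affected**

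Secondary endpoints are per-protocol, which requires more than 75% of study drug and no major deviation (SAP 2.5). Assuming a constant infusion over five days:

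- Threshold: 0.75 × 120 h = 90 h.
- Discharge at 48 h: 48/120 = 40%; at 60 h: 50%; at 72 h: 60%. All fail.
- Discharge at 96 h: 96/120 = 80%. This passes the drug criterion.

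Patients who complete five days and return by day 30 or day 90 can stay in the per-protocol set, and whether their readmission days count is undefined.

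**4. The route to the primary analysis**

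The primary analysis is by intention to treat. SAP 6.1 fits a mixed model with treatment, time point and their interaction, and tests the 48 h difference only if that model gives significance. It does not list the time points in the model or the term that must be significant. If the daily scores are used, the filled 72 to 120 h values are part of the gate, although the 48 h value is not altered.

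**5. Size**

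The only yardstick in the plan is its design difference of 25 points with SD 40. Its sample size reproduces: 2 × (1.960 + 0.842)² × 40²/25² = 40.2, so 41 per group, set at 45. The documents give no readmission rate, readmission length or PASS at readmission, so the rest is assumption.

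Understatement of one arm's mean PASS at a late time point = (patients readmitted in the window / 45) × points by which LOCF is too low:

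| Readmitted of 45 | 50 points | 100 points | 150 points |
|---|---|---|---|
| 1 | 1.1 | 2.2 | 3.3 |
| 2 | 2.2 | 4.4 | 6.7 |
| 4 | 4.4 | 8.9 | 13.3 |
| 6 | 6.7 | 13.3 | 20.0 |

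Understatement of an arm's mean stay, if readmission days are not counted = proportion readmitted × mean days:

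| Proportion | 3 days | 7 days | 14 days |
|---|---|---|---|
| 5% | 0.15 | 0.35 | 0.70 |
| 10% | 0.30 | 0.70 | 1.40 |
| 20% | 0.60 | 1.40 | 2.80 |

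The comparison between arms is biased only to the extent that these amounts differ between arms. The PASS table also needs discharge and return within 48 to 120 h, a far narrower window than 90 days, so its lower rows are extreme.

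**The case against.** A reader might infer that a patient discharged at 60 h and readmitted on day 4 for 8 days is scored as a 2.5-day success when the true total is 2.5 + 8 = 10.5 days. The documents do not support that, for two reasons. Nothing says that length of admission is the index stay only; a 90-day look-up, together with the protocol's total duration, is compatible with counting the later days. And this patient has had 50% of the drug, so is outside the per-protocol length-of-stay comparison altogether. SAP 6.3 also treats early discharge under major protocol deviations, which may exclude further patients.

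Nor is the primary value at 48 h replaced by a carried-forward score. Other planned data would show some deterioration: PASS at day 14, Atlanta severity from the medical files, and 90-day mortality. SAP 6.3 allows for other imputation if its assumption fails. Readmission is not a named endpoint in Protocol 7.4.2, and its omission from the SAP does not cancel its collection.

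All of this limits the point but does not remove it. The stay variable is still undefined, so the choice could be made after the data are seen. The imputation clause depends on many values being missing through severe disease, names no method, and is not triggered by a readmission. The early-discharged patients remain in the intention-to-treat PASS model. The per-protocol rule also means that readmission would be poorly seen if it were compared only in that set.

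**Conclusion.** The point holds in a limited form. The SAP omits, without explanation, the readmission data that the protocol collects. It leaves open whether length of admission includes readmission days. It applies LOCF on an assumption of low disease activity with no rule for a patient known to have returned.

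The consequences fall in two places: on late PASS values in the intention-to-treat mixed model that gates the 48 h test, provided that model uses the daily scores; and on length of stay for patients who remain per-protocol. The observed 48 h score is sound.

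The size cannot be stated from the documents. The ranges of 1.1 to 20 points and 0.15 to 2.8 days are arithmetic on assumed rates and show only that the effect could be trivial or could approach the 25-point design difference at a late time point. This is worth correcting before unblinding; it does not invalidate the primary endpoint.

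**What to change.** - Restore readmission to SAP Table 2, and list it as an outcome in SAP 2.2 and Table 1.
- In SAP 6.2, compare the proportion readmitted by day 30 and by day 90 with Fisher's exact test in all randomized and treated patients, because the per-protocol set removes many of the early-discharged patients concerned.
- Define length of admission as total hospital days to day 90 including readmissions, in line with Protocol 9.1.2, and name one starting point: SAP 2.2 counts the 90 days from admission, SAP Table 1 from randomization.
- In SAP 6.3, for a patient readmitted before 120 h, use PASS scored from the readmission records where available. Otherwise treat the score as missing in the mixed model rather than carrying the pre-discharge score forward.

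The cost is SAP wording, one or two extra tables and a more variable length-of-stay outcome. Two practical limits should be stated. PASS needs self-reported pain and tolerance of solid food (SAP Table 1), which may not be available at readmission, and both documents currently treat these patients as lost to follow-up for daily PASS, so scoring at readmission needs a data-collection instruction as well as SAP text. Data collection also ends for patients treated for less than 48 h, so including them in the readmission comparison requires the 30- and 90-day record look-up to continue for them.
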